10.4.5 Supportive analyses

Not applicable.

10.5 Secondary objectives

10.5.1 Key secondary objective(s)

The key secondary objective of this study is to assess Overall Response (OR) of Partial Response (PR) or Complete Response (CR) based on local investigator assessment.

For patients with solid tumors the assessment criteria will be RECIST 1.1 and will include responses of CR and/or PR. For hematologic tumors other appropriate hematological response criteria will apply and are included in the appendices.

The overall response rate (PR plus CR) and its 95% exact confidence interval will be provided for each patient group. In the event where sample size in each patient group is small (<10), only ORR summary for the entire study cohort will be presented.

10.5.2 Other secondary efficacy objectives

The secondary objectives of the study:

- To assess progression free survival (PFS) based on local investigator assessment per RECIST 1.1 or other appropriate hematological response criteria
- To assess overall survival
- To assess duration of response (DOR) based on local investigator assessment per RECIST 1.1 or other appropriate hematological response criteria
- To assess safety and tolerability

The secondary efficacy variable progression free survival (PFS) is defined as the time from the date of first dose to the date of first documented disease progression or relapse or death due to any cause.

PFS will be summarized and graphed using the Kaplan-Meier product-limit method for the entire study cohort. For cohorts with at least 10 subjects, separate PFS analyses will be conducted for each cohort. Patients who drop-out without progression will be censored at the time of last adequate assessment. The estimates of the 25th, median, 75th percentiles of the PFS and their 95% confidence intervals will be provided, if applicable.

Overall survival (OS) is defined as the time from the date of first dose to the date of death due to any cause. If a patient is not known to have died, survival time will be censored at the date of the last contact.

OS will be summarized and graphed using the product-limit method as above.

The duration of response applies only to patients whose best response was PR or CR. For patients with solid tumors the assessment criteria will be RECIST 1.1 and will include responses of CR and/or PR. For hematologic tumors other appropriate hematological response criteria will apply and are included in the appendices. The duration of response is defined as the time from the first documented response to the date first documented disease progression or relapse or death due to any cause. The duration of response will be summarized descriptively for the entire study cohort.

If the study primary efficacy endpoint is not met, Novartis may decide not to conduct some of the above secondary efficacy analyses but instead provide those endpoints in listings only.

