The primary efficacy objectives of the study, clinical benefit (definition details see Section 6.1) associated with ceritinib treatment based on local investigator assessment, will be summarized. The clinical benefit rate will be analyzed using a Bayesian hierarchical model to evaluate trial success and futility, and the relationship between relevant pathway regulation and the response to treatment with ceritinib (if applicable). Analysis details are documented in Section 10.

Duration of response (DOR) based on local investigator assessment will be analyzed. In the event of a low response rate, DOR will be listed only without frequency summaries. Overall response (OR) will be summarized with the number and percentages of subjects for each response category (e.g., for solid tumor - CR, PR, SD, PD, Not evaluable). Progression-free survival (PFS) will be summarized using Kaplan-Meier (KM) methodology. Due to limited survival follow-up for the study, overall survival will only be descriptively summarized, ie, only the frequency of deaths will be provided.

Subject demographics, disease characteristics (including mutation analyses), ceritinib treatment, and safety variables will be summarized descriptively, by nominal visit (if applicable), and/or overall.

Data used for the analyses specified in this document will come from the Electronic Data Capture (EDC) system. In addition, the mutation data from the central laboratory will be collected in an Excel spreadsheet format and subsequently be uploaded to a secure FTP site by Novartis.

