2.1 Change in planned analyses from the protocol

The protocol specifies that analyses are to be conducted by "patient group" which is formed by the types of cancer at study entry. That is, subjects with the same tumor type will be considered as in the same "patient group". For efficacy analyses, with exception of the primary analysis of clinical benefit rate (i.e., summarized by 'patient group'), other descriptive summaries in general will be produced overall for all ceritinib-treated subjects. Separate summaries may be produced for those groups with at least 10 subjects. All subjects will be combined for any safety analyses.

[figure not shown]
In the event of a low response rate, DOR will only be listed, and not tabulated. Subjects who had no disease progression/death will be censored at last adequate tumor assessment on or before the discontinuation/completion of the study.

For determination of PFS events, due to tumor assessments post study treatment are not collected, deaths occurred more than 30 days post treatment without prior progressive disease/relapse of disease will not be considered as an event.

For overall survival analysis, no KM method will be used due to early study termination. Descriptive summaries will be provided instead.

For vital signs, values will be descriptively summarized by nominal visit. Separate summaries of significant abnormalities will not be provided, but will be reflected in adverse events (AEs).

For cardiac imaging, due to data collection is only as clinically indicated, thus only listing will be provided.

3 Subjects and treatments

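### Duration of response is censored, but the plan gives it only a descriptive or frequency summary, so no stated method uses the censoring

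*Protocol*

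**What the plan says.** Protocol 10.5.2 treats DOR as a time-to-event variable: "The duration of response is defined as the time from the first documented response to the date first documented disease progression", with relapse or death from any cause also ending it. The same section assigns methods to the other two time-to-event endpoints. For progression-free survival (PFS): "PFS will be summarized and graphed using the Kaplan-Meier product-limit method for the entire study cohort". For overall survival (OS): "OS will be summarized and graphed using the product-limit method as above". For DOR it says: "The duration of response will be summarized descriptively for the entire study cohort". Protocol 10.4.4 gives censoring rules for PFS and OS and does not mention DOR.

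The SAP fills part of the gap. In 2.1, directly after the sentence on DOR, it states: "Subjects who had no disease progression/death will be censored at last adequate tumor assessment on or before the discontinuation/completion of the study". On output, SAP Section 2 says: "In the event of a low response rate, DOR will be listed only without frequency summaries"; 2.1 repeats the point: "In the event of a low response rate, DOR will only be listed, and not tabulated". What counts as a low response rate is not defined. SAP Section 6 has subsections for clinical benefit rate (CBR), overall response, PFS, OS and CBR by gene mutation, but none for DOR. It names Kaplan-Meier for PFS only.

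**The concern.** A response that is ongoing at the last adequate scan has a duration known only to exceed the observed time. Once a censoring rule is set, the summary has to use it. Here the rule exists but the named summaries, descriptive statistics or frequencies, have no place for it. A programmer left to choose could follow the general default in SAP Section 4 for continuous data (mean, standard deviation, median, quartiles) or the similar list in protocol 10.2. Both sit in baseline sections, but nothing different is specified for DOR.

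Censoring is likely to matter. The protocol's primary report cut-off (4.2) requires only the opportunity for 16 weeks of treatment. SAP 2.1 notes that tumor scans after treatment are not collected, so a responder who stops without progressing is also censored. At stake is how a reader judges the durability of any response seen, including against the phase I figures in protocol 1.2.4.1.1, which give an estimated median, a median not reached and a 12-month rate.

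**Working it through.** The plan states no target, event count or power for DOR, so there is no figure of its own to reproduce. The check has two parts.

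**1. Does descriptive plausibly mean Kaplan-Meier here?** Protocol 10.5.2 names the product-limit method for PFS and OS and uses a different word for DOR. SAP 2.1 withdraws Kaplan-Meier for OS and substitutes descriptive summaries, so it sets the two against each other. SAP Section 2 says what that means for OS: "overall survival will only be descriptively summarized, ie, only the frequency of deaths will be provided". At endpoint level, descriptive is therefore an alternative to Kaplan-Meier.

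**2. How large could the bias be if a plain median were reported?** Inputs from the documents:
- first scan at 8 weeks (protocol 4.1.1), taken as the time of response;
- cut-off 16 weeks after last entry (protocol 4.2);
- accrual of 24 months (protocol Appendix Q, 14.17.1.2), with 12 months as a sensitivity case;
- true median m of 9.69 or 7.39 months (protocol 1.2.4.1.1), or 19.45 months from the 12-month DOR rate of 65.2%: 12 × ln 2 / (−ln 0.652) = 19.45.

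Assumptions: exponential DOR, uniform accrual, and censoring at the cut-off rather than at the last scan before it.

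Follow-up after response is uniform from a = 16 − 8 = 8 weeks = 1.84 months to b = a + accrual, which is 25.84 months for 24-month accrual. With λ = ln 2 / m:
- share censored = [exp(−λa) − exp(−λb)] / [λ(b − a)];
- the naive median t, with censored times taken as complete, solves exp(−λt) × (b − t)/(b − a) = 0.5.

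For m = 9.69, λ = 0.0715. Share censored = (0.877 − 0.158)/(0.0715 × 24) = 0.42. At t = 6.6, 0.624 × (25.84 − 6.6)/24 = 0.624 × 0.802 = 0.50, so the naive median is 6.6 months.

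Simulation of 400,000 responders per setting (Kaplan-Meier on 20,000 of them) gave, in months:

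| True median | Accrual | Censored | Median, all times as complete | Median, completed responses only | Kaplan-Meier |
|---|---|---|---|---|---|
| 7.39 | 24 | 33.5% | 5.59 (−24%) | 4.47 (−39%) | 7.36 |
| 7.39 | 12 | 50.5% | 4.61 (−38%) | 3.10 (−58%) | 7.38 |
| 9.69 | 24 | 41.9% | 6.61 (−32%) | 5.02 (−48%) | 9.62 |
| 9.69 | 12 | 58.8% | 5.16 (−47%) | 3.32 (−66%) | 9.69 |
| 19.45 | 24 | 62.9% | 9.21 (−53%) | 6.20 (−68%) | 19.91 |
| 19.45 | 12 | 76.1% | 6.32 (−67%) | 3.71 (−81%) | not reached |

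The direction is always downward. The gap narrows with a shorter true DOR and widens with shorter follow-up. With only 20 responders and a true median of 9.69, Kaplan-Meier gives no median in about 3% (24-month accrual) or 32% (12-month accrual) of simulated trials.

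**The case against.** A reader might infer that the trial will report a median DOR and that it will be too short by about a third. The documents do not support that. Neither promises a median DOR; the SAP speaks of frequency summaries or a listing, and a listing with censoring marked carries no such bias. The defaults that include a median are written for baseline data. This part of the objection stands.

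The month figures also have limits. The borrowed medians come from ALK-positive lung cancer, which this trial excludes, and Amendment 1 describes the patients enrolled as heavily pretreated, so true DOR may be shorter. The calculation uses the protocol's primary cut-off. The SAP analyzes data at database lock after early termination by the sponsor, and the protocol provides for later data in an addendum (4.2) and a final report (6.3.3). This also stands, and confines the figures to illustration.

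SAP Section 2 calls all non-primary analyses descriptive, which includes Kaplan-Meier PFS, so the word could be stretched to cover Kaplan-Meier for DOR. This is weaker, because the text on individual endpoints draws the contrast shown above. Nor does setting a censoring rule show that the summary will use it.

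Finally, the listing fallback for few responders already exists. That is correct; only a censoring flag would be new.

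**Conclusion.** The point holds as a gap in method: DOR has a censoring rule and no stated summary that uses it. If a plain median were reported, the shortfall would be 24% to 67% with censored times taken as complete, and 39% to 81% with completed responses only, across the settings above. These ranges rest on exponential DOR, the assumed accrual and cut-off, and medians from an excluded population. Only the downward direction carries over to this trial; the size does not.

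A reader might also infer that the trial's conclusions are at risk. They are not: group success and futility under protocol 10.4.3 depend on the posterior probability for CBR alone. DOR is an other secondary endpoint, the SAP gives no power consideration to secondary objectives (Section 9), and protocol 10.5.2 allows some secondary efficacy endpoints to be listed only if the primary endpoint is not met. This is a worthwhile, low-cost improvement.

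**What to change.** In protocol 10.5.2 and a new DOR subsection of SAP Section 6:
- estimate DOR among responders (confirmed responders, for solid tumors) by Kaplan-Meier, applying the SAP 2.1 censoring rule to DOR by name;
- report the median with its 95% CI, allowing it to be not reached, and the numbers of events and censored;
- drop means, medians and duration-category counts that ignore censoring;
- keep the listing-only option when responders are few, state the number that triggers it, and add a censoring flag to each listed duration.

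The cost is a few lines of text. The PFS program can be reused, and no new data are needed.

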10.5.3 Safety objectives

For all safety analyses, the safety set will be used. All listings and tables will be presented by patient groups.

The assessment of safety will be based mainly on the frequency of adverse events and on the number of laboratory values that fall outside of pre-determined ranges. Other safety data (e.g., electrocardiogram, vital signs) will be considered as appropriate. All safety data will be listed.

The safety summary tables will include only assessments collected no later than 30 days after study treatment discontinuation. Those collected later than 30 days after study treatment discontinuation will be flagged in listings.

10.5.3.1 Analysis set and grouping for the analyses

10.5.3.1.1 Adverse events (AEs)

All adverse events recorded during the study will be summarized. The incidence of treatment-emergent adverse events (new or worsening from baseline) will be summarized by system organ class and/or preferred term, maximum severity (based on CTCAE v4.03), type of adverse event, relationship to the study treatment by treatment group. Deaths reportable as SAEs and non-fatal serious adverse events will be listed by patient and tabulated by type of adverse event and patient group.

Adverse events will be summarized by presenting the number and percentage of patients by system organ class and/or preferred term, the maximum severity (based on CTCAE v4.03) and treatment arm. Adverse events related to study treatment will also be summarized. In addition, adverse events of related nature may be analyzed by categories regrouping the relevant preferred terms, as appropriate.

10.5.3.1.2 Laboratory abnormalities

All laboratory values will be converted into SI units and the severity grade will be calculated using appropriate common terminology criteria (CTCAE v4.03).

A severity grade of 0 will be assigned when the value is within normal limits. For lab parameters for which severity grades are determined both through normal limits and absolute cut-offs, in the unlikely case when a local laboratory normal range overlaps into the higher (i.e. non-zero) CTCAE grade, the laboratory value will still be taken as within normal limits and assigned a CTCAE grade of zero.

A listing of laboratory values will be provided by laboratory parameter, patient, and treatment arm. A separate listing will display notable laboratory abnormalities (i.e., newly occurring CTCAE grade 3 or 4 laboratory toxicities). Lab values collected later than 30 days after study treatment discontinuation will be flagged in the listings.

The following by-group summaries will be generated separately for hematology, and biochemistry parameters:

[figure not shown]
- shift tables using CTCAE grades to compare baseline to the worst on-treatment value
- for laboratory tests where CTCAE grades are not defined, shift tables using the low/normal/high/(low and high) classification to compare baseline to the worst on-treatment value.
- listing of all laboratory data with values flagged to show the corresponding CTCAE grades and the classifications relative to the laboratory normal ranges.

[figure not shown]
10.5.3.1.3 Other safety data

Summary statistics for data from other tests will be provided, notable values will be flagged, and any other information collected will be listed as appropriate.

Descriptive summary statistics will be provided for :

- Electrocardiograms: changes from baseline to last available ECG results
- Cardiac imaging: number and percentage of patients with notable LVEF values
- Vital signs: number and percentage of patients with at least one post-baseline vital sign abnormality
- ECOG performance status: shift table comparing baseline to worst post baseline ECOG performance status.
- All other safety related procedures as required
- Listings with flagged notable values and any other information collected will be provided as appropriate.

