6.4.3.6 Herbal medications

Herbal preparations/medications are not allowed throughout the study, as a potential drug-drug interaction is always possible. These herbal medications include, but are not limited to: St. John's wort, Kava, ephedra (ma huang), gingko biloba, dehydroepiandrosterone (DHEA), yohimbe, saw palmetto, and ginseng.

Patients should stop using herbal medications at least 7 days prior to first dose of ceritinib treatment.

6.4.3.7 Medications that may prolong the QT interval or have a known risk of inducing Torsades de Pointes

Ceritinib has potent activity on the hERG channel with an IC₅₀ of 0.4 µM. However, there were no ceritinib -related effects *in vivo* in monkeys at doses as high as 100 mg/kg (human equivalent dose (HED) of 1950 mg).

Serial ECGs were collected following a single dose and at steady-state to evaluate the effect of ceritinib on the QT interval in an open-label, dose-escalation, and expansion study [[CLDK378X2101](#)]. A total of 304 patients were treated with ceritinib doses ranging from 50 to 750 mg with 255 patients treated with ceritinib 750 mg. One of 304 patients (<1%) was found to have a QTc >500 msec and 10 patients (3.3%) had an increase from baseline QTc >60 msec. A central tendency analysis of the QTc data at average steady-state concentrations demonstrated that the upper bound of the 2-sided 90% CI for QTc was 16 msec at ceritinib 750 mg. A PK/PD analysis suggested concentration-dependent QTc interval prolongation.

Concomitant administration of ceritinib with drugs known to have a high risk of increasing the QTc interval and drugs known to increase the QTc interval that are also primarily metabolized by CYP3A4/5 should be avoided. Concomitant use of ceritinib and any medication included in [Table 14-16 of Appendix P](#) titled “List of prohibited QT prolonging drugs” (i.e., drugs that are generally accepted by the Qtdrugs.org Advisory Board of the Arizona CERT to have a known risk of causing Torsades de Pointes) is not permitted.

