7.1.3 End of treatment visit, including premature withdrawal and study discontinuation visit

7.1.3.1 End of treatment (EOT) visit

Patients who completely discontinue study treatment should be scheduled for an End of Treatment (EOT) visit within 7 days following the date study treatment is permanently discontinued, at which time all of the assessments listed for the EOT visit will be performed. For details of assessments, refer to [Table 7-1](#). If the decision to withdraw the patient occurs at a regularly scheduled visit, that visit may become the EOT visit rather than having the patient return for an additional visit.

An End of Treatment Phase Disposition eCRF page should be completed, giving the date and reason for stopping the study treatment. If a study withdrawal occurs, or if the patient fails to

return for visits, the investigator must determine the primary reason for a patient's premature withdrawal from the study and record this information on the End of Treatment Phase Disposition eCRF page.

End of treatment/Premature withdrawal visit is not considered as the end of the study.

For patients with a best response of SD or better who discontinued study treatment due to disease progression, an optional tumor sample should be obtained for genomic analysis.

At a minimum, all patients who discontinue study treatment, including those who refuse to return for a final visit, will be contacted for safety evaluations during the 30 days following the last dose of study treatment.

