7.2.2.7 Cardiac assessments

7.2.2.7.1 Electrocardiogram (ECG)

A standard 12-lead ECG will be performed at screening, Day 1 of Cycles 1 and 2, at Day 1 of every other cycle and at EOT according to the Visit Schedule outlined in [Table 7-1](#).

The interpretation of the tracing must be made by a qualified physician and documented in the ECG section of the eCRF. Each ECG tracing should be labeled with the study number, patient initials (if permitted by local regulations), Patient Number, date, and kept in the source documents at the study site. Only clinically significant abnormalities should be reported in the Adverse Events eCRF. Clinically significant abnormalities present when the patient signed informed consent should be reported on the Medical History eCRF page. Clinically significant

findings must be discussed with the Novartis Medical Monitor prior to enrolling the patient in the study. New or worsened clinically significant findings occurring after informed consent must be recorded on the Adverse Events eCRF page.

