7.5 Other safety evaluations

ECOG performance status will be summarized by visit for SS. The number and percentage of subjects in each score (0-5) will be displayed. In addition, the shift table of ECOG value from baseline to the worst score post baseline will be presented.

ECG values will be summarized descriptively by visit for the SS. Change from baseline for each collected parameter will also be summarized. The ECG parameters to be summarized include: QTcF, HR, PR, QT, and QRS.

Cardiac imaging evaluations will only be listed.

Baseline for the safety evaluation is defined as the last non-missing measurement on or prior to the first ceritinib dose.

8 Interim analyses

Scheduled interim analysis is planned for the primary endpoint of clinical benefit rate only as required by the Bayesian Hierarchical design. The first interim analysis performs after the first 30 patients have been dosed for at least 16 weeks or discontinued then every 13 weeks thereafter until study enrollment closure. After that, one CBR analysis will be done after database lock. Interim analyses may be performed more frequently dependent on enrollment rate to avoid over-enrollment in any of the disease groups. At each interim analysis, the groups will be evaluated for early futility and early success by comparing posterior quantities for the response rate to pre-specified early stopping criteria.

There is no plan for a formal interim analysis of safety or other secondary endpoints for this study. However, for publication or other purposes, interim data review of clean data will be performed as necessary. At these interim reviews, patient demographics/baseline characteristics, the primary and secondary endpoints as applicable, and all important safety endpoints will be summarized. No formal report will be issued for these interim data reviews.

9 Determination of sample size

The sample size was chosen by the usual criteria of obtaining adequate power for the alternative hypothesis of interest as shown in the protocol Tables 4.2 of Appendix Q (same as Table 2 as shown below in Section 10.4.2). This hypothesis corresponds to a generally effective treatment across groups and incorporates variation in treatment effects to reflect the realistic expectation that treatment effects may differ by group. In this setting, analytical power calculations are not possible, but the design was simulated to obtain the power of the

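### No planned ECG or vital-sign table counts patients with outlying values or uses the worst on-treatment value, so some QTcF findings can go uncounted

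*Protocol*

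**What the plan says.** Protocol Section 10.5.3.1.3 gives ECG a single summary: "Electrocardiograms: changes from baseline to last available ECG results". Vital signs, in the same list, get a patient count: "Vital signs: number and percentage of patients with at least one post-baseline vital sign abnormality". ECOG status gets a shift table to its worst value. Laboratory data (Protocol 10.5.3.1.2, SAP 7.4) get shifts to the worst on-treatment grade. The protocol adds "Listings with flagged notable values and any other information collected will be provided as appropriate", but states no ECG threshold for a notable value.

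SAP Section 7.5 says "ECG values will be summarized descriptively by visit for the SS". It adds change from baseline and names QTcF, heart rate, PR, QT and QRS. SAP Section 2.1, which sets out departures from the protocol, does not mention this change. It does declare the one for vital signs: "Separate summaries of significant abnormalities will not be provided, but will be reflected in adverse events (AEs".

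Other parts of the protocol bear on the point:
- Table 3-1 lists ECG and vital-sign change among the safety endpoints and refers to CTCAE v4.03.
- Section 8.2 names QT prolongation and bradycardia as events of special interest.
- Section 6.4.3.7 reports the phase I ECG results as patient counts: 1 of 304 with QTc above 500 ms and 10 of 304 with an increase above 60 ms. It also states: "A PK/PD analysis suggested concentration-dependent QTc interval prolongation".
- Table 7-1 schedules an ECG at the end-of-treatment (EOT) visit, which Section 7.1.3.1 places "within 7 days following the date study treatment is permanently discontinued".
- Section 7.2.2.7.1 says of ECG findings: "Only clinically significant abnormalities should be reported in the Adverse Events eCRF".

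**The concern.** For a drug with a known QTc signal, the useful safety question is how many patients crossed a threshold at any time on treatment. A last-value change does not answer it, and neither does a set of per-visit distributions. The last ECG is a poor choice in particular. It may be taken after dosing has stopped, or after a QTc prolongation has resolved during a dose hold.

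Two things are at stake. Modest prolongation that neither changed dosing nor was judged clinically significant may not be counted in any table. And the study's results could not be set beside the phase I figures the protocol itself quotes, because no planned table has the same form.

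**Working it through.** **1. Which planned output counts patients by worst ECG value?**
- Protocol ECG item: last value only, so no.
- SAP 7.5: descriptive by visit, so no. SAP Section 2 speaks of nominal visits. The repeat ECGs that Table 6-3 calls for around a QTc of 501 ms or more therefore have no stated place.
- Protocol vital-sign item: a patient count, which SAP 2.1 withdraws.
- SAP 7.3: minimum and maximum of pulse at each scheduled visit. This shows an extreme, not how many patients had one.
- SAP 7.1 and 7.1.1: patient counts, but only of what was reported as an adverse event (AE).

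**2. What does the AE route catch?** Protocol Section 8.1.1 makes a test abnormality an AE if it is symptomatic, clinically significant, needs therapy or changes study medication. Applying Table 6-3:
- QTc of 501 ms or more on at least two ECGs: dose omitted, so an AE.
- Graded bradycardia, even Grade 1 or 2: dose omitted, so an AE.
- QTc 450-480 ms and 481-500 ms: dose maintained, so an AE only by symptoms, need for therapy or investigator judgement.
- A rise above 60 ms that stays below 501 ms: addressed only when it comes with serious arrhythmia, so otherwise as in the previous line.

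The gap is the last two lines.

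**3. How many patients could fall there?** The protocol's own percentages reproduce: 1/304 = 0.33% and 10/304 = 3.29%. At most one of the ten patients with a rise above 60 ms can also have exceeded 500 ms, so at least 10 − 1 = 9 of the ten did not.

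Assume the phase I rates apply to the planned 70-90 patients:
- Rise above 60 ms, expected number: 70 × 10/304 = 2.3 and 90 × 10/304 = 3.0.
- Chance of at least one: 1 − (1 − 10/304)^70 = 0.90 and 1 − (1 − 10/304)^90 = 0.95.
- The exact 95% interval for 10/304 is 1.6% to 6.0%. That gives 70 × 0.0159 = 1.1 up to 90 × 0.0597 = 5.4 patients.
- QTc above 500 ms: 70 × 1/304 = 0.23 and 90 × 1/304 = 0.30 expected. The chance of at least one is 0.21 to 0.26.

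**4. Would the average reveal one such patient?** A single 60 ms rise moves a visit mean by 60/70 = 0.86 ms or 60/90 = 0.67 ms if everyone attends that visit. The visit maximum, if shown, would display it, but not whether the maxima at different visits come from one patient or several.

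**5. How far off drug can the last ECG be?** Up to 7 days (168 h). The fraction of drug remaining then depends on the half-life assumed:
- Single-dose half-life of 31-41 h (Protocol 1.2.4.1.2): 2^(−168/31) = 0.02 to 2^(−168/41) = 0.06.
- Half-life scaled by the fall in apparent clearance, 88.5/33.2 = 2.67 (an assumption), giving 83-109 h: 0.24 to 0.34.
- Half-life implied by the accumulation ratio of 6.2 under simple once-daily accumulation (an assumption): daily fraction retained 1 − 1/6.2 = 0.839, and 0.839^7 = 0.29.

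The range is too wide to support more than this: a day-7 ECG understates on-drug exposure by an uncertain amount.

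**The case against.** A reader might infer that the planned summaries cannot show outliers at all. They can, by several routes:
- The findings that change dosing become AEs by rule. They are then counted by preferred term and maximum severity, in the special-interest summary, and in the table of events leading to dose adjustment or interruption.
- SAP 7.3 explicitly gives minimum and maximum pulse. The SAP Section 4 convention for continuous data also includes minimum and maximum. It is stated for baseline data but is plausibly meant for ECG too.
- SAP Section 2 lists all data.

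For the same reasons it would be wrong to read SAP 7.5 as means only, or to say that a low pulse need not appear in any table.

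A reader might also infer that most patients' last ECG is off drug. The documents do not support that. Seven days is an upper limit, and Section 7.1.3.1 lets a regular visit serve as the EOT visit. The SAP's by-visit summary also covers ECGs taken during treatment, which weakens the last-ECG criticism if the SAP governs.

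Finally, the SAP does deliver change from baseline, as Table 3-1 asks. The vital-sign change is declared openly. This is a single-arm signal-seeking study that was terminated early, so the counts will be small and the listings readable.

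All of this stands as a limit on the point. It does not supply the missing output. A visit extreme is not a patient count, a listing is not a summary, and the AE route rests on investigator judgement for the findings identified above. Table 3-1 also refers to CTCAE grading, which laboratory data receive in a table and ECG does not.

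**Conclusion.** The point holds in limited form. No planned ECG or vital-sign table counts patients with outlying values or uses the worst on-treatment value. The protocol's last-ECG measure may be taken up to 7 days off drug or after recovery from a dose hold. The SAP's by-visit summary replaces it without being listed in SAP 2.1, and the protocol's one patient count, for vital signs, is withdrawn.

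The practical gap is asymptomatic QTcF findings with no dosing consequence: 481-500 ms, or a rise above 60 ms staying below 501 ms. These can surface only as visit extremes, in listings, or as AEs if judged clinically significant. The size is about 2 to 3 patients with a rise above 60 ms among 70-90, assuming phase I rates carry over and enrolment is as planned. The SAP records early termination, and the expected count scales with the number treated. No efficacy result or design figure is affected. This is a worthwhile, inexpensive improvement to safety reporting.

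**What to change.** 1. In SAP 7.5, add the number and percentage of patients by worst on-treatment post-baseline QTcF, including unscheduled ECGs. Use categories already in the protocol: the Table 6-3 QTc grades, and above 500 ms and an increase above 60 ms as in Section 6.4.3.7. State whether a single reading of 501 ms or more counts, since Table 6-3 asks for two ECGs.
2. Restore the protocol's number and percentage of patients with any abnormal vital sign after baseline. The sponsor should set the cut-offs in advance. The 60 bpm value in Table 6-3 is a recovery criterion and should not be taken over as a definition of abnormality.
3. Present EOT ECGs taken after the last dose separately, and define the on-treatment window for ECG.
4. List the move from last-ECG change to by-visit summaries in SAP 2.1.

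The cost is one or two extra tables and some SAP wording, with no new data collection. The downside for the sponsor is that the safety tables may look slightly less favourable.
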